6 STUDY ASSESSMENTS

Assessment	Screening & Enrolment	Randomisation (baseline) Day 0	Day 1 - 5	Day 3 (range 2 - 5)	Day 30	Day 120
Assessment of eligibility criteria	Х					
Written Informed Consent	Х					
Demographic Data, Contact details, GP details, PMH, CFS, AMTS or AMT4		х				
Intraoperative data		х				
Blood sample- Haemoglobin	Х	х		Х		
Blood sample - U&E's		х		Х		
ECG		х		Х		
Blood sample - Troponin		х	XX*			
4AT		х	XX*			
Blood transfusions. Pre and post transfusion haemoglobins					х	
Hospital length of stay					х	
Readmission					х	Х
Complications including MACE					Х	
Mortality					Х	Х
EQ5D5L		Х			Х	Х
Health services utilisation questionnaire					х	х

6.1 STUDY ASSESSMENTS

*Blood sampling for troponin analysis and 4AT to be performed twice in days 1 to 5, ideally on the 1st and 3rd calendar days after randomisation, with all blood samples being at least 24h apart from each other.

6.2 LONG TERM FOLLOW UP ASSESSMENTS

Participants will be prospectively followed up in person or by accessing paper and electronic records until acute hospital discharge or 30 days post-randomisation, by the research team. The research team will access hospital records for up to 120 days to capture data regarding cardiac events and other complications, hospital readmissions and mortality. Where a participant has died the cause of death will be recorded from the death certificate.

Survival status will be confirmed by the participating sites, by checking hospital records, prior to attempting to contact the participant in hospital or by telephone at home at 30 and 120 days to administer EQ-5D-5L and health economic follow up questionnaires. In participants who have

CR007-T02 v0.5 Page **34** of **69**

IRAS 299977/308830

Version 5.0 26Jun2024

not regained capacity before discharge from hospital, the research team will attempt to gain consent as described in section 4.2.2.3. Where capacity has been regained the research team will contact the participant to administer the questionnaires. Where capacity has not been regained, the research team will contact the participant's representative to ask them to complete the questionnaires on behalf of the participant. If the research team is unable to contact the participant, or their representative, by telephone, the questionnaires will be posted.

6.3 STORAGE AND ANALYSIS OF SAMPLES

Blood samples for full blood count and urea and electrolytes will be collected at randomisation, then on post randomisation day 3 (window day 2 - 5) and thereafter at the discretion of the clinical team. These will be analysed locally in routine NHS laboratories as part of routine care, and the results recorded in the CRF by the local study team.

The serum troponin measurement will be used to define the primary endpoints and secondary endpoints relating to cardiac complications. Blood will be taken for serum troponin measurement at randomisation, then twice more in days 1 to 5, ideally on the 1st and 3rd calendar days after randomisation with all samples being at least 24h apart from each other. Where possible these will be timed with routine blood sampling as part of normal clinical care. These samples will be drawn by venepuncture (or by arterial or central venous catheter if available) into serum gel. Blood should be allowed to clot for a minimum of 30 minutes then spun as soon as possible, ideally within 2 hours of sample collection. If serum gel is not available at a site, Lithium-Heparin tubes can be used, and separate instructions will be issued for sample processing.

Samples should be labelled and stored at -70C or lower until they are transported to Edinburgh for analysis. Study samples will be shipped from site and stored centrally. Frequency of shipments will be agreed on a per-site basis. Samples will be sent on dry ice to the University of Edinburgh centralised storage When ready for analysis samples will be defrosted at room temperature for 60-120min, mixed well with vortex then centrifuged. Laboratory staff will aliquot 320 μ l from the original tubes to Eppendorf tubes and set in the centrifuge basket before spinning at 3000 G, 6 degrees for 10 minutes.

The ARCHITECTSTAT high-sensitive cardiac troponin I (Troponin) assay (Abbott Laboratories, Abbott Park, IL, USA) will be used for sample analysis in this study and has a limit of detection of 1.2 ng litre⁻¹ and an inter-assay coefficient of variation of <10% at 4.7 ng litre⁻¹. The mean concentration for a healthy reference population is 1.6 (3.1) ng litre⁻¹, and the 99th percentile URL for the whole population is 26 ng litre⁻¹ (females, 16 ng litre⁻¹; 34 males, ng litre⁻¹).

Depending on time, biomarker required and availability of storage, samples will be stored for bona fide research purposes for a period 5 years after the study end date.

IRAS 299977/308830

Version 5.0 26Jun2024

7 DATA COLLECTION

7.1 DATA COLLECTION

The following data will be collected from participants in RESULT-Hip.

Screening Data

Anonymised screening data will be recorded on screening logs and entered onto the database by research teams at site. This data will be used to generate a CONSORT diagram at the end of the trial

At enrolment (pre-consent)

- Participant Name
- Participant Contact details
- Personal Consultee Name and Contact details (if appropriate)
- date of admission
- Date of birth

At Randomisation:

- Age
- Gender
- Pre-existing cardiovascular disease
- haemoglobin

At Baseline or as soon as available afterwards.

- CHI or NHS number
- ethnicity (using British Census 2021 categories)
- residential status (own home/sheltered housing, residential care, nursing care)
- pre-fracture mobility status (see NHFD proforma APPENDIX D)
- Abbreviated Mental Test Score (AMTS) or AMT4
- fracture type (see NHFD proforma APPENDIX D)
- date of surgery
- ASA-PS
- type of anaesthesia (general, spinal, other regional)
- operation performed
- duration of surgery
- preoperative haemoglobin
- haemoglobin after surgery (PACU, Recovery Ward, Ward on operative day)
- number of allogeneic units of blood transfused intraoperatively
- G number as a record of all red cell transfusions administered
- Use of blood sparing management technology or therapies
- history of dementia
- pre-existing malignancy
- pre-existing cardiovascular disease

CR007-T02 v0.5 Page **36** of **69**

IRAS 299977/308830

Version 5.0 26Jun2024

- cardiovascular risk factors (vascular disease, diabetes, hypertension, kidney disease)
- presence of atrial fibrillation
- cardiac medications
- anticoagulant and anti-platelet medications
- Creatinine and eGFR
- Troponin
- 12-lead electrocardiogram
- Nottingham Hip Fracture Score (33)
- Rockwood Clinical Frailty Scale
- 4 'A's Test (4AT) for delirium
- EQ-5D-5L

Post randomisation the following will be collected:

- Haemoglobin and U&E's, one measurement days 2 5. Where possible these will be timed with existing blood sampling.
- pre and post transfusion haemoglobin (each transfusion episode, according to transfusion guidelines)
- Two blood samples for troponin for batch analysis in Edinburgh
- ECG on the 3rd day (window day 2 5) following randomisation
- Number of units of blood transfused following first time of Hb less or equal to 90 g. L⁻¹
- Volume of blood transfused (ml) following first time of Hb less or equal to 90 g. L⁻¹
- G number as a record of all red cell transfusions administered
- AKI (KDIGO criteria) (from review of paper and electronic case notes)
- Delirium (via 4AT) twice in days 1 5 following randomisation (supplemented by review of paper and electronic case notes)
- All post-operative complications using Hip Fracture Post-Operative Morbidity Survey (Appendix A)
- Episodes of chest pain days 0 3

At 30 days post randomisation the following will be collected:

- G number as a record of all red cell transfusions administered
- length of hospital stay
- Major adverse cardiac events (MACE) including myocardial infarction (from review of paper and electronic case notes
- New MINS
- Copy of any non-trial cardiac investigations carried out locally e.g. angiogram, echocardiograph uploaded to CRF
- New stroke*
- New pulmonary embolus*
- All complications (Appendix A)
- AKI using KDIGO definitions

IRAS 299977/308830

Version 5.0 26Jun2024

- Mortality
- EQ-5D-5L
- Health services utilisation (HE questionnaire)

At 120 days post randomisation the following will be collected:

- Acute hospital discharge destination
- Emergency readmission
- Readmission specialty and location
- Mortality
- Cause of death (if applicable)
- Re-operation
- Total number of hospital, ICU, HDU bed days.
- Place of residence (using NHFD)
- Mobility (using NHFD)
- EQ-5D-5L
- Health services utilisation (HE Questionnaire)

*Definition of stroke or pulmonary embolus is "confirmation by the clinical team that the patient has had a stroke or pulmonary embolus".

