1.4.2 Secondary Endpoints

Secondary outcomes at 30 days are as follows:

- 1. All-cause mortality
- 2. New Myocardial Injury post-randomisation (New MINS)
- 3. Individual MACE components (including type of arrhythmia)
- 4. Complications (including AKI, infection, delirium)
- 5. Proportion of participants transfused; volume of blood transfused per patient
- 6. Discharge destination (home, other hospital, nursing home, other)
- 7. Acute hospital length of stay
- 8. ED-5D-5L

Additional secondary outcomes at 120 days are as follows:

- 1. All cause mortality
- 2. Secondary care costs
- 3. Unplanned hospital readmissions
- 4. Mobility (as defined by NHFD or SHFA dataset
- 5. Residential status (as defined by NHFD or SHFA dataset)
- 6. EQ-5D-5L
- 7. Health services resource use

Clinical outcomes will be measured until acute hospital discharge or 30 days post randomisation whichever is soonest. Death, readmission, mobility, residential status, quality of life and resource use will be measured at 120 days post-randomisation.

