2.3 DURATION OF PARTICIPANT INVOLVEMENT

[figure not shown]
We will screen people with hip fracture who meet the age inclusion criteria. This can take place from the time the patient enters the hospital and up to and including 7 days post –surgery. Once potential participants have been identified they will be followed daily to check the haemoglobin level measured on their blood results. If a haemoglobin measurement triggers inclusion in the study, that is, if the Hb falls to 90 g.L⁻¹ or less, then the patient will be randomised. Randomisation should take place as soon as possible after the triggering haemoglobin measurement and no later than post-operative day 8. This can occur pre-operatively or postoperatively whenever on the patient journey that the Hb value first falls to 90 g.L⁻¹ or less.

Participants who are randomised in the study follow one of two arms: restrictive or liberal blood transfusion. Both arms have the same measurements, data collection and follow up. The participants will be in the study for up to 120 days from entry. Participants will be sent a summary of the study results at the end of the trial by the University of Edinburgh if permission is given to do so. Thereafter there will be no further participant-researcher interactions.

IRAS 299977/308830

Version 5.0 26Jun2024

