4.3 RANDOMISATION

Participants should be randomised as soon as possible after the triggering haemoglobin measurement and no later than post-operative day 8.

Participants will be randomised by remote computer to ensure allocation concealment. Allocation will be in a 1:1 ratio with stratification by centre, age (<80 vs. \geq 80 years) and preexisting diagnosis of cardiovascular disease. Randomisation will be performed using a webbased randomisation system developed by the Edinburgh Clinical Trials Unit (ECTU).

Due to the nature of the intervention blinding of trial participants and local study teams will not be possible, however the primary outcome assessment will be adjudicated by a panel blinded to treatment allocation.

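### Section 7.1 counts transfused units and volume from the first Hb of 90 g/L or less, under a post-randomisation heading, so units given before allocation can enter a secondary outcome

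*Protocol*

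**What the plan says.** Section 1.4.2 names the 30-day secondary outcome as "Proportion of participants transfused; volume of blood transfused per patient". For the window it gives only an end: "Clinical outcomes will be measured until acute hospital discharge or 30 days post randomisation whichever is soonest". The schedule in section 6 places blood transfusions in the Day 30 column and also gives no start.

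The only start point in the protocol is in section 7.1. Under the heading "Post randomisation the following will be collected" it lists "Number of units of blood transfused following first time of Hb less or equal to 90" g/L and "Volume of blood transfused (ml) following first time of Hb less or equal to 90" g/L.

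That Hb is the randomisation criterion (section 3.4). It can occur at any time from admission, including before surgery (section 2.3). On the interval that follows, section 4.3 says: "Participants should be randomised as soon as possible after the triggering haemoglobin measurement and no later than post-operative day 8". Section 2.3 says the same, and neither sets a limit in hours. Sections 1.2.3 and 5.2.1 start the two transfusion strategies at randomisation.

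Section 7.1 also lists, among the baseline items, "number of allogeneic units of blood transfused intraoperatively". It records the G number of every red cell transfusion.

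**The concern.** The heading and the items beneath it give different start points. One is randomisation. The other is the trigger Hb, which always comes first. A site that follows the item wording counts units given before the participant had an allocation, and a site that follows the heading does not.

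Transfusion in the gap is possible under the protocol. No exclusion criterion in section 3.5 bars it. The gap can include the operation when the trigger is preoperative, and consent through a consultee or relative can lengthen it (sections 4.2.3.1 and 4.2.3.2). Sections 1.1.3 and 1.1.4 report that many clinicians transfuse above 70 g/L.

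These outcomes show whether the two strategies delivered different exposure. Units given before allocation cannot be an effect of it. They add to both arms alike and hide part of the contrast on some scales.

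There is also an overlap. An intraoperative unit given after the trigger fits both the baseline intraoperative item and the count from the trigger, so it could be recorded twice.

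**Working it through.** The protocol states no figure for transfusion exposure or for separation between arms, so there is none to reproduce. The check concerns direction and plausible size.

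**Inputs**
- From the protocol: 1:1 allocation (section 4.3); the count starts at the first Hb of 90 g/L or less (section 7.1); the intervention starts at randomisation (sections 1.2.3 and 5.2.1); non-normal continuous outcomes are analysed non-parametrically (section 9.2).
- Assumed: the proportion transfused after randomisation, p_L = 95% in the liberal arm and p_R = 30% in the restrictive arm (50% as an alternative); and q, the share transfused between trigger and randomisation, at 10% and 20%. Randomisation makes q equal across arms in expectation.

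**Proportion transfused**

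If transfusion in the gap and after randomisation are independent, the counted proportion in an arm is 1 − (1 − p)(1 − q). The difference between arms is then (1 − q)(p_L − p_R).

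| p_L vs p_R | q | Liberal counted | Restrictive counted | Difference |
|---|---|---|---|---|
| 95% vs 30% | 0 | 95% | 30% | 65 points |
| | 10% | 1 − 0.05 × 0.90 = 95.5% | 1 − 0.70 × 0.90 = 37% | 58.5 points |
| | 20% | 1 − 0.05 × 0.80 = 96% | 1 − 0.70 × 0.80 = 44% | 52 points |
| 95% vs 50% | 0 | 95% | 50% | 45 points |
| | 10% | 95.5% | 1 − 0.50 × 0.90 = 55% | 40.5 points |
| | 20% | 96% | 1 − 0.50 × 0.80 = 60% | 36 points |

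Most of the distortion is in the restrictive arm, because nearly all liberal participants are already counted as transfused.

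**Units and volume**

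Let m be the mean units given in the gap, equal in both arms in expectation. The counted mean difference is (μ_L + m) − (μ_R + m) = μ_L − μ_R. It does not change, and this needs no independence assumption. The ratio (μ_L + m)/(μ_R + m) moves towards 1.

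A simulation with 400,000 participants per arm illustrates this. It assumed 95% vs 35% transfused after randomisation. Units per transfused participant were 1 + Poisson(0.6) in the liberal arm, 1 + Poisson(0.3) in the restrictive arm and 1 + Poisson(0.3) for gap transfusions. The rank measure is the probability that a liberal participant receives more than a restrictive one, with ties counted as half.

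| q | Difference in proportion | Mean difference (units) | Ratio of means | Rank measure | Standardised difference |
|---|---|---|---|---|---|
| 0 | 60 points | about 1.07 | 3.3 | 0.83 | 1.38 |
| 10% | 54 points | about 1.07 | 2.8 | 0.81 | 1.21 |
| 20% | 48 points | about 1.07 | 2.5 | 0.79 | 1.11 |
| 30% | 42 points | about 1.07 | 2.3 | 0.78 | 1.05 |

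The ratios agree with hand arithmetic. The means are 0.95 × 1.6 = 1.52 and 0.35 × 1.3 = 0.455. At q = 10%, m = 0.10 × 1.3 = 0.13, and 1.65/0.585 = 2.82.

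**The case against.** The case on the other side is substantial.

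**Section 7.1 is a data-collection list, not an endpoint definition.** Section 1.4.2 does not mention the first Hb of 90 g/L or less, and the derivation may be settled in an analysis plan that is not shown. A reader might infer that the protocol plainly scores pre-allocation units as outcomes. It does not go that far: the heading says post-randomisation, so the text conflicts with itself, and applying the same start to proportion transfused is an inference. What stands is that section 7.1 holds the only start point given. If the heading governed, the phrase about the first Hb would serve no purpose.

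**The protocol works to keep the gap short.** Randomisation is to be prompt, pre-consent is sought early (section 4.2.2), and a nominated consultee can act where no personal consultee is available in time (section 4.2.3.1). This stands: q may be close to zero.

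**Not every measure of separation shrinks.** A reader might infer that the whole reported contrast is diluted. The mean difference in units or volume is not. For the same reason a bias in the blood-cost comparison is not supported: section 9.3 reports differences in means and costs the whole surgical admission.

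**Theatre units of participants randomised before surgery are not lost.** A reader might infer that listing them at baseline drops them from the outcome. Such a participant had the trigger Hb before surgery, so those units fall inside the count as worded. The remaining fault is the double listing.

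**A correct count may be recoverable.** G numbers are collected, and the 24- and 48-hour rules in sections 5.2.1 and 13.2.1 depend on transfusion timing. That holds if a date and time are kept with each unit, but section 7.1 lists no such field.

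**Conclusion.** The point holds as a conflict over where the count starts. As worded, the unit and volume items can take in red cells given before allocation, and an intraoperative unit can be recorded under two items.

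The difference in proportion transfused would shrink by the factor (1 − q), provided the same start is applied to that outcome. Under the assumed 95% vs 30%, this is a loss of 6.5 points at q = 10% and 13 points at q = 20%. Ratios and rank comparisons are attenuated too, and the latter matter because section 9.2 sends skewed outcomes to non-parametric methods. The mean difference is unbiased but less precise.

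The size rests on assumed transfusion rates, on independence between gap and later transfusion, and on q, which the protocol does not give. The effect is negligible if randomisation follows the trigger promptly. The primary outcome, its ranking and the sample size are unaffected. This is an inexpensive correction to a secondary process measure and no threat to the trial's main conclusion.

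**What to change.** In section 7.1, define number of units, volume and proportion transfused as red cells started after the date and time of randomisation, up to acute discharge or day 30. State the same start in section 1.4.2.

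Record units given between the first Hb of 90 g/L or less and randomisation as a separate baseline item.

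Classify each intraoperative unit as baseline or outcome according to whether it was given before or after randomisation, so that none is counted in both.

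The cost is a wording change and a derivation rule. It needs the transfusion date and time held with each G number, which is at most one extra field per unit, with no new visits or samples.

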7.2 SOURCE DATA

Source documents will include:

- Paper medical records
- Electronic medical records
- Electronic laboratory results
- Paper electrocardiographs
- EQ-5D-5L and HE questionnaires
- Death certificates

7.3 SOURCE DATA DOCUMENTATION

Data will be inputted by the local research team directly into the electronic database or will be collected on case report forms and paper questionnaire proformas before being entered into the secure, trial specific database using REDCAP: Research Electronic Data Capture (Vanderbilt University, USA). This is a secure, password protected platform, hosted on University of Edinburgh servers.

IRAS 299977/308830

Version 5.0 26Jun2024

8 DATA MANAGEMENT

8.1 PERSONAL DATA

[figure not shown]
The following personal data will be collected as part of the research:

- Participant name, address, telephone number and participant representative details (if appropriate), will be recorded on a contact details CRF and stored securely within the ECTU study database to facilitate central follow up by the research team at each site. Access to contact details data will be minimised and only accessible to those with delegated responsibility. Personal data will be stored for a minimum of 5 years after the study end date.
- Patient initials will be recorded on screening logs and stored securely within the ECTU REDCAP database for the purpose of monitoring and reporting patient flow through the trial via the production of a CONSORT diagram.
- Patient gender, date of birth and National Health Service (NHS) number, hospital number, Community Health Index (CHI) number, or other unique hospital identifier will be recorded and stored securely within the ECTU REDCAP database for the purposes of statistical analysis and correct identification of patients by research teams for follow up.
- Personal data will be stored at site by research teams on NHS computers (desktop and laptop). Computers will be password protected and kept in locked offices. All paper files containing personal data will be held in a secure location according to local NHS/University policies, as applicable.
- Personal data entered onto the ECTU REDCAP database will be hosted securely on University of Edinburgh servers. Only approved delegated members of the local research team or wider study team will have access to personal data.

Baseline and follow up data to 120 days, including de-identified scans of ECG's and other cardiac investigations e.g. angiogram, will be collected by the local research team at each site and entered onto /uploaded to the ECTU REDCAP database. The local research team can only view the records of patients from their own centre.

IRAS 299977/308830

Version 5.0 26Jun2024

8.2 TRANSFER OF DATA

Data collected or generated by the study (including personal data) will not be transferred to any external individuals or organisations outside of the Sponsoring organisation unless part of the trial. or without specific prior ethical approval.

Blood samples for troponin analysis will be transferred from sites by secure courier to the University of Edinburgh for analysis.

